7. GENERAL ASPECTS FOR STATISTICAL ANALYSIS

The statistical principles applied in the design and planned analyses of this study are consistent with International Conference on Harmonization (ICH) E9 guidelines (ICH 1998).

7.1. General Methods

Assessments of all study endpoints (as listed in Section 4.2 will be summarized descriptively. Formal hypothesis testing will not be performed.

In general, categorical variables will be reported as frequency and percent. Continuous variables will be reported as the number of participants, mean, standard deviation (SD), or standard error (SE), median, minimum and maximum or range.

For quantitative measures, change from baseline will be calculated as: Change from baseline = test value at Visit X – test value at baseline

All data will be summarized in tables with a single "overall" column for statistics. As applicable, data will be summarized by visit and/or study period.

All summaries, statistical analyses, and individual participant data listings described below will be completed using Version 9.4 or later of the SAS Statistical Analysis System (SAS Institute, Inc. Cary, NC).

7.2. Baseline and Study Day Definitions

7.2.1. Baseline

For all safety assessments and effectiveness summaries across the study, study baseline will be defined as the last non-missing measurement collected/ assessed during the Baseline (Xyrem) Period in which participants remain on a stable Xyrem dose and regimen, with or without concomitant anticataplectics or stimulants. First dose of XYWAV will be administered in the first night of Visit 3. Assessment and data collected in the baseline period up till that night, will be included in this period.

7.2.2. Study Day

The screening period is from Day -30 to Day -1. The 2-week baseline period is Day 1 to Day 14. Participants on a stable dose and regimen of Xyrem will be switched to XYWAV treatment at the beginning of the Intervention (Open-label Conversion and Treatment Optimization) period, starting the night of Visit 3/Day 15 and continue through to the End of Treatment (ET) (Visit 8) or Early Discontinuation (E/D) visit, as applicable.

Study day will be calculated as:

Study Day = (the date of assessment or event - the first day of the baseline period (Visit 2)) + 1 XYWAV Study Day = (date of assessment - date of first dose of XYWAV) + 1

7.2.3. Visit Windows

Except where specified, all data will be summarized using the CRF visit at which the data was collected. Where data is captured at an Early Termination visit, those data will be summarized with the regular visit at which the assessment would have been captured, relative to the study period during which the participant withdrew. For example:

- If a participant early discontinues during the Baseline Period, i.e. prior to the first dose of XYWAV, then data should be mapped to Visit 3.
- If a participant early discontinues during the Intervention Period, i.e. after at least one dose of XYWAV, then data should be mapped to the next scheduled visit at which those data would have been captured, based on the Schedule of Assessments.

For data captured independent of a CRF visit, eg, Adverse Events, Concomitant Medications and Cataplexy Diary, the following rules will apply:

- If the reported date is on or prior to first dose of XYWAV then the data will be considered to be included into the Xyrem Baseline Period for summaries
- If the reported date is after the first dose of XYWAV while on or prior to the completion of treatment or early discontinuation, then the data will be considered to be included into the XYWAV Intervention Period for summaries.

Unscheduled visits in general will not be mapped (excluded from analyses) when the corresponding scheduled visit is present. Unscheduled visits will only be mapped when the scheduled visit is missing. If more than 1 unscheduled assessments are available, choose the one with the assessment date closer to the target study day specified below, if 2 assessments are equally close to the target day (but on different sides), the latter assessment will be chosen. In addition, unscheduled visits with the assessment date earlier than the date of first dose of XYWAV, or participants early discontinue the study prior to the first dose of XYWAV, the data can only be mapped up to Visit 3. If the assessment date is later than the date of first dose of XYWAV, the unscheduled data should not be mapped to any visit prior to Visit 3.

Study Period	Study Visit	Target Study Day
Baseline	Visit 2	1
Intervention	Visit 3	15

Intervention	Visit 4	22
Intervention	Visit 5	29
Intervention	Visit 6	36
Intervention	Visit 7	43
Intervention	Visit 8	57

Where summaries require a period of time, eg, the last week of a study period, this will be determined based on the actual visit date, as long as the above rule is maintained. For example, if a participant has a first dose of XYWAV on Day 15 and Early Terminates on Day 20, the last week of XYWAV will be only Days 16-20, as the participant received Xyrem on Days 14 and 15 (the first dose of XYWAV being taken the night of Day 15). Imputation due to the missing data this approach generates will follow rules outlined in Section 7.2.4.

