9.4.1.2. Definition of Study Periods for Analysis

The Baseline (Xyrem) Period refers to a 2-week duration in which participants remain on a stable Xyrem dose and regimen, with or without concomitant anticonvulsants or stimulants. All data collected prior to the participant's first dose of XYWAV will be included in this period.

The Intervention (Open-label Treatment Conversion and Optimization) period refers to the 6-week duration in which the participant's treatment is transitioned from Xyrem to XYWAV. All data collected after the first dose of XYWAV will be included in this period (which does not include the Safety Follow-up period).

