9.4.4. Safety And Tolerability Analysis

All safety and tolerability analyses will be conducted in the Safety Population, based on key endpoints are summarized below. Additionally collected safety data will be summarized, as appropriate.

Adverse Event Analyses

AEs will be mapped to system organ classes (SOC) and preferred terms (PT) in alignment with Medical Dictionary for Regulatory Activities (MedDRA) criteria. AEs are defined in this study as follows ([Appendix 7](#)).

- A ‘Xyrem-emergent AE’ refers to an AE that began or worsened in the period following signing of the informed consent and before administration of the first study intervention (XYWAV) dose (ie, including the Screening period through the Baseline [Xyrem-stable dose and regimen] period)
- A treatment-emergent adverse event (TEAE) refers to an AE that either began or worsened after administration of the first dose of study intervention drug (XYWAV) to ET (prior to the Safety Follow-up period).
- Unless specified, the term AE will include both Xyrem-emergent AEs and TEAEs
- Any AEs occurring in the post-intervention Safety Follow-up period will not be considered as either Xyrem-emergent AEs or TEAE; these will not be included as part of safety and tolerability analyses, but listed separately.

Xyrem-emergent AEs (overall and during the Baseline period), TEAEs, SAEs, AEs leading to discontinuations and fatal AEs will be summarized. All AEs will be summarized by maximum severity.

The population incidence of Xyrem-emergent AEs, TEAEs, SAEs, AEs leading to discontinuations and any fatal AEs will be presented by MedRA SOC and PT categories. PT summaries may also be provided, as appropriate.

If a participant has multiple events with the same PT occurring in different periods, the event will be reported for each of those periods. Multiple increases in severity will only be counted as one AE.

Nausea Visual Analog Scale (NVAS)

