10.2. Adverse Events

Adverse events (AEs) occurring from the initial participant ICF signature date until the end of Safety Follow-up visit will be reported. If the Investigator becomes aware of a serious adverse event (SAE) within 30 days after the last dose of study drug XYWAV, the event must also be reported. In addition, any SAE assessed as related to study drug or procedure by the Investigator must be reported regardless of time elapsed after study termination.

Adverse events recorded in the case report form will be coded to system organ class (SOC) and preferred term using the Medical Dictionary for Regulatory Activities (MedDRA), Version 24.0. The investigator will assess the relationship of each AE to study drug. AE with a missing relationship to study drug will be reported as related in the summaries. Severity, as determined by the Investigator using National Cancer Institute (NCI) common terminology criteria for adverse events (CTCAE) version 5.0 or higher, will be classed as mild, moderate, severe, life-threatening or fatal. An AE with missing severity will be reported as missing in the summaries.

Note that participants who acquire COVID-19 or report AEs due to the COVID-19 public health emergency (eg anxiety) while on study will be coded accordingly and included in the adverse event summaries.

AEs are defined in this study as follows (Protocol Appendix 7):

- A 'Xyrem-emergent AE' refers to an AE that began or worsened in the period following signing of the informed consent and before administration of the first study intervention (XYWAV) dose (i.e., including the Screening period through the Baseline [Xyrem-stable dose and regimen] period till the first dose of XYWAV)
- A treatment-emergent adverse event (TEAE) refers to an AE that either began or worsened after administration of the first dose of study intervention drug (XYWAV) to End of Treatment (ET) period (prior to the Safety Follow-up period).
- Safety follow-up AEs are defined as occurring after the last dose date until 30 days after the last dose date
- Unless specified, the term AEs will include both Xyrem-emergent AEs, TEAEs and Safety follow-up AEs.
- Safety follow-up AEs will not be considered as either Xyrem-emergent AEs or TEAE. They will not be included into summary tables but will be presented in listings.
- Xyrem-emergent AE related summaries will be based on safety analysis set.
- TEAE related summaries will be based on XYWAV Safety analysis set.

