An overall summary on Xyrem-emergent AE and TEAE with following categories will be provided:

- Subjects with any Xyrem-emergent AE/TEAE
- Subjects with any drug-related Xyrem-emergent AE/TEAE
- Subjects with any serious Xyrem-emergent AE/TEAE
- Subjects with any Xyrem-emergent AE/TEAE by severity
- Subjects with any Xyrem-emergent AE/TEAE with outcome as death
- Subjects with any Xyrem-emergent AE/TEAE leading to drug withdrawal
- Subjects with any Xyrem-emergent AE/TEAE leading to drug dose reduction
- Subjects with any Xyrem-emergent AE/TEAE leading to drug dose increase
- Subjects with any Xyrem-emergent AE/TEAE leading to drug interruption

In addition, subject incidence of Xyrem-emergent AEs/TEAEs will be summarized by following:

- SOC and PT
- PT only
- Maximum Severity by SOC and PT
- Drug-related by SOC and PT
- Xyrem-emergent AE/TEAE leading to drug withdrawal by SOC and PT

For data listings, all following will be presented:

- All AEs
- AEs with an outcome of death
- AEs leading to drug withdrawal
- Serious AEs

If a participant has multiple events with the same PT occurring in different periods, the event will be reported for each of those periods. Participant incidence of AEs by SOC and PT tables are sorted by SOCs (alphabetical order) and then by PTs (descending order) within each SOC for the overall frequency. For summaries by PT only, PTs will be sorted in descending order of overall frequency.

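### SAP 7.2.3 puts adverse events dated on the day of the first XYWAV dose in the Xyrem period, SAP 10.2 splits at the dose itself, and neither is said to govern

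*SAP*

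**What the plan says.** SAP 7.2.3 (Visit Windows) sets a rule for data captured outside a CRF visit. It gives AEs, concomitant medications and the cataplexy diary as examples, and it works on the reported date: "on or prior to first dose of XYWAV then the data will be considered to be included into the Xyrem Baseline Period". Later dates, up to completion or discontinuation, go to XYWAV. The worked example in the same section counts by calendar day. Day 15 is Xyrem and XYWAV starts on Day 16, "as the participant received Xyrem on Days 14 and 15 (the first dose of XYWAV being taken the night of Day 15".

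SAP 10.2 defines the AE classes by the dose, not the date. A treatment-emergent AE (TEAE) "refers to an AE that either began or worsened after administration of the first dose of study intervention drug (XYWAV"; a Xyrem-emergent AE is one before that dose. Protocol 9.4.4 has the same boundary: "began or worsened after administration of the first dose of study intervention drug (XYWAV) to ET (prior to the Safety Follow-up period". Protocol 9.4.1.2 says of the Intervention period: "All data collected after the first dose of XYWAV will be included in this period". SAP 7.2.1 ends the baseline at the night of the first dose: "Assessment and data collected in the baseline period up till that night, will be included in this period".

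SAP Appendix 1.1 imputes incomplete AE start dates. Four branches set the start to exactly the first XYWAV dose date:

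1. Year missing, with the end date missing or on/after the first dose.
2. Month missing, in the year of the dose.
3. Day missing, in the month of the dose.
4. All other cases.

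A start imputed later than the AE end date is reset to the end date. SAP 7.6 lists changes to the analysis sets and the severity reference, and nothing about AE periods.

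**The concern.** Two rules in one SAP cover the same event and can place it under different drugs. AEs are the first-listed key endpoint. In a single-arm switch study, the Xyrem-emergent/TEAE label is the only thing that separates the two drugs in the AE tables. The period also enters the tables directly. SAP 10.2 states: "If a participant has multiple events with the same PT occurring in different periods, the event will be reported for each of those periods". Protocol 9.4.4 plans a summary by period: "Xyrem-emergent AEs (overall and during the Baseline period), TEAEs, SAEs, AEs leading to discontinuations and fatal AEs will be summarized".

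Two programmers who each follow the SAP could therefore produce different tables. Read literally and applied to imputed dates, 7.2.3 moves AEs of uncertain onset out of the XYWAV column and into the Xyrem column, a direction that favours XYWAV.

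**Working it through.** The plan gives no event count, AE rate or missing-date rate on this point, so there is no figure of its own to reproduce. The check has four parts.

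**1. Observed dates.** The first dose is taken at night (SAP 7.2.1, 7.2.2). An onset earlier that day is Xyrem under both rules, and an onset after midnight carries the next date and is XYWAV under both. Only onsets from the dose to midnight differ. If the dose is taken between 21:00 and 24:00 (assumption), that is 3/24 to 0/24 of the date, or 12.5% to 0%.

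**2. Imputed dates.** I applied Appendix 1.1 to fifteen missing-date patterns, with illustrative dates (consent 10 August 2021, first dose 15 September 2021, last study date 10 November 2021).

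| Result | Patterns | Under 7.2.3 | If first-dose date means TEAE |
|---|---|---|---|
| Start stays on first-dose date (branches 1 to 3) | 6 | Xyrem | TEAE |
| Start reset to an end date before the dose (branches 2 and 3) | 2 | Xyrem | Xyrem |
| Start set to another date | 7 | same under both | same under both |

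None of these patterns reaches the fourth branch, but its text assigns the first-dose date directly.

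The missing-year rule shows the apparent intent. It sends the AE to the consent date if it ended before the dose, and otherwise to the first-dose date. If the first-dose date means Xyrem, both outcomes fall under Xyrem and the split never changes the drug. It does so only if the first-dose date means XYWAV.

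**3. Day-missing onsets in the dose month.** Assume a dose day d uniform on 1 to 30 and uniform onset.

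- After the dose, mean of min(30−d, L): 10.5 days for L = 14, so 10.5/14 = 75%; 14.5 days for L = 42, so 14.5/42 = 35%. Under 7.2.3 these XYWAV onsets go to Xyrem. The end-date reset cannot reduce the share, because an event that starts after the dose cannot end before it.
- Before the dose, mean of min(d−1, L): 10.5 days for L = 14 (75%); 14.5 days for L = 44, screening plus baseline (14.5/44 = 33%). If the first-dose date means TEAE, these are ceilings, because the reset returns every AE that ended before the dose to Xyrem. If half had ended (assumption), 75% becomes 37.5%.
- Share of these imputed onsets truly on XYWAV, at equal daily AE rates: at least 14.5/(14.5+14.5) = 50%, or 14.5/(14.5+10.5) = 58% if only the 14 baseline days contribute. With half of the earlier AEs ended: 14.5/(14.5+7.25) = 67% and 14.5/(14.5+5.25) = 73%. If the XYWAV daily rate is half the Xyrem rate, the floors are 7.25/(7.25+14.5) = 33% and 7.25/(7.25+10.5) = 41%.
- With 28- or 31-day months, the 75% becomes 73% or 76%.

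**4. Effect per event.** One moved event changes an overall incidence line by at most one subject: 1/100 = 1 point per column, or 1/90 = 1.1 points if 90 participants reach XYWAV (assumption). The change is zero if the participant already counts in both columns through other events.

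**The case against.** The strongest reply is that SAP 10.2 is the AE-specific section, repeats the protocol's definitions, and defines the classes used in every AE table it lists. On that reading, 7.2.3 only labels study periods, its worked example concerns last-week windows, and 7.6 had no AE change to record. With night-time dosing, a date rule that gives the whole day to Xyrem is also right for most of its hours. Moreover, 7.2.3 speaks of reported dates, and an imputed date is not reported. The protocol's Baseline-period AE summary does not reappear in SAP 10.2. Finally, the study is descriptive, AEs are collected at every visit, and few onset dates may be incomplete.

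Much of this stands. The conflict for observed dates is narrow, the step to imputed dates is an inference, and 10.2 is probably what was meant. But 7.2.3 names AEs, and no sentence subordinates it. Even under 10.2 alone, an onset imputed to the first-dose date has no clock time, so it is neither before nor after the dose, and no section settles its class.

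A reader might also infer that an AE between the last dose and the End of Treatment visit is both a TEAE and a follow-up AE, because the two windows use different end points. SAP 10.2 rules this out: it places follow-up AEs in neither class and shows them only in listings.

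**Conclusion.** The inconsistency is real and should be settled before the AE tables are run, but its effect is likely to be small. The documents establish that two AE rules differ on the first-dose date, that no precedence is given, and that four imputation branches land on that date. They do not establish how many AEs are affected, or that 7.2.3 will be applied to imputed dates.

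A reader might infer that treating these AEs as TEAEs corrects a known bias. The documents do not support that. It is a conservative convention that matches the apparent purpose of Appendix 1.1. Whether it is nearer the truth depends on the unknown AE rates and on how many earlier AEs had ended by the dose.

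The narrow window for observed dates assumes a first dose before midnight, as in the SAP's Day 15 example. A dose recorded after midnight would carry the next date and widen the window. The percentages rest on uniform dose days and onsets and apply only to AEs with a missing onset day.

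**What to change.** - Remove AEs from the on-or-before rule in SAP 7.2.3, and state that SAP 10.2 governs the period of an AE. The rule can stay for the cataplexy diary.
- State that an AE whose onset is imputed to the first XYWAV dose date is a TEAE. No further exception is needed, because the existing reset keeps AEs that ended before the dose as Xyrem-emergent.
- For an observed onset on that date, use the onset time if it is recorded; otherwise count the AE as a TEAE.
- Report how many AEs rest on an imputed or untimed first-dose date.

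The cost is a few sentences of SAP text, one derivation line and one count. The downside is that some baseline-onset AEs that are still ongoing at the dose, or have no end date, will count as TEAEs; the ceilings in part 3 of the check bound this for day-missing onsets. Untimed observed onsets on the first-dose date will also count as TEAEs, although most hours of that date precede the dose. The reported count lets a reader judge both.

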10.6. Vital Signs

The following vital signs measurements will be reported for this study.

- Sitting systolic blood pressure (SBP), (millimeter of mercury [mmHg])
- Sitting diastolic blood pressure (DBP) (mmHg)
- Sitting heart rate (beats per minute [bpm])
- Sitting respiratory rate (breaths/minute)

• Body Temperature (°C)

These vital signs will be measured during the screening visit and each in-clinic scheduled visit, according to the schedule of activities.

The observed and change from baseline vital signs across all study periods will be summarized by visit. Change from XYWAV Conversion Day will also be summarized for visits after conversion. In addition, number and percentages of subjects with at least one abnormal vital signs (based on criteria at Table 4 below) will be summarized by visit.

A listing of vital signs with flagged abnormal values will also be presented.

Table 4 Vital Signs Predefined Markedly Abnormal Criteria

Parameter (unit)	Low	High
SBP (mmHg)	< 90 mmHg	> 140 mmHg; > 160 mmHg
DBP (mmHg)	< 50 mmHg	> 90 mmHg; > 100 mmHg
Heart rate (bpm)	< 60 bpm	> 100 bpm
Respiratory Rate	< 12 breaths/min	> 20 breaths/min
Temperature (°C)	< 36.0 °C	> 38.0 °C

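### SAP 7.2.3 lets an on-XYWAV unscheduled reading fill a missing pre-dose Visit 3, which can distort the vital-signs change from XYWAV Conversion Day

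*SAP*

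**What the plan says.** **Timing of Visit 3.** SAP 7.2.1 states: "First dose of XYWAV will be administered in the first night of Visit 3". It places data collected up to that night in the Xyrem period, and under it "study baseline will be defined as the last non-missing measurement collected/ assessed during the Baseline (Xyrem) Period". Protocol 9.4.1.2 likewise assigns everything before the first XYWAV dose to Baseline.

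**Period label.** The target-day table in SAP 7.2.3 has the row "Intervention Visit 3 15". SAP 7.2.2 adds: "The 2-week baseline period is Day 1 to Day 14", which by day count leaves Day 15 outside Baseline.

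**Unscheduled readings (SAP 7.2.3).** They are used only when the scheduled visit is missing. Among several candidates the one nearest the target day is taken, and if two are equally near on opposite sides the later one wins. Readings before the first XYWAV dose may go no later than Visit 3. For readings after it, the text says only that "the unscheduled data should not be mapped to any visit prior to Visit 3".

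**Use of the conversion value.** SAP 10.6 summarizes vital signs by visit and as change from baseline, and adds: "Change from XYWAV Conversion Day will also be summarized for visits after conversion". The SAP does not define XYWAV Conversion Day.

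**The concern.** Visit 3 is the last scheduled contact on Xyrem and the natural reference for change after the switch. A mapping rule should therefore close it to readings taken on XYWAV. This rule closes only the visits before it, so Visit 3 can be filled from either side of the first dose. A participant whose Visit 3 value comes from an on-XYWAV reading would have XYWAV compared with XYWAV in the vital-signs change from conversion. The Visit 3 row of the by-visit tables, including the counts of abnormal values, would also hold a mixture of Xyrem and XYWAV readings.

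The Intervention label adds to the doubt. A programmer who works from the table could treat Visit 3 as post-switch, while one who works from 7.2.1 would treat it as pre-switch. Blood pressure is one of the vital signs, and the protocol's introduction rests part of the case for XYWAV on sodium and blood pressure.

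**Working it through.** There is no planned figure to reproduce: the study is descriptive and the SAP gives no rate of missing visits. The check applies the rules as written.

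1. **Is Visit 3 pre-dose?** Yes. SAP 7.2.1 and 7.2.2 and the protocol's schedule footnote all start XYWAV on the night of Visit 3 (Day 15). The example on last-week windows in SAP 7.2.3 itself counts Day 15 as a Xyrem day. The date rule in 7.2.3 for diary, adverse-event and medication data assigns dates up to and including the first dose to the Xyrem period. The Intervention label in the table conflicts with all of these as a classification of data.

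2. **Which visits may an unscheduled reading fill?** The target days are 1, 15, 22, 29, 36, 43 and 57 for Visits 2 to 8.
   - Dated before the first dose: Visit 2 or 3.
   - Dated after the first dose: Visit 3 or later.
   - Dated on the first-dose day: neither limit applies.

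   Visit 3 is in both of the first two sets.

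3. **Choice between candidates** (first dose Day 15, Visit 3 reading missing; distance = |day − 15|):
   - Day 13 (Xyrem) and Day 17 (XYWAV): |13 − 15| = 2 and |17 − 15| = 2. This is a tie on opposite sides, so the later is taken: Day 17, on XYWAV.
   - Day 12 (Xyrem) and Day 17 (XYWAV): 3 against 2. Day 17 is nearer and is taken.

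4. **How far after the dose?** The midpoint between the Visit 3 and Visit 4 targets is (15 + 22)/2 = 18.5, so Days 16 to 18 lie nearer to Visit 3. With a first dose on Day 16, the same holds for Days 17 and 18. This midpoint is only a guide: the closeness rule chooses among readings for a missing visit and does not assign a reading to its nearest visit. The SAP sets no outer limit, so later readings are not excluded either. The text permits these mappings by omission and does not direct them.

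5. **Which outputs use a mapped Visit 3 value?**
   - Diary, adverse-event and medication data: split by date of first dose.
   - NVAS: last 7 days of each period.
   - ESS: baseline visit and end of treatment, with study baseline fixed by 7.2.1.
   - PGIc, ease-of-switching and preference questionnaires: end of treatment or early discontinuation.
   - Vital signs: by visit, and as change from XYWAV Conversion Day. These are exposed.

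6. **Size.** Number affected = N × P(Visit 3 reading missing) × P(post-dose unscheduled reading, given missing). N is about 100 from the protocol; both probabilities are assumptions.
   - Low: 100 × 0.02 × 0.05 = 0.1.
   - High: 100 × 0.05 × 0.20 = 1.
   - Ceiling at 5% missing, if every such participant had a qualifying reading: 100 × 0.05 × 1 = 5.

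   If a fraction f has a fully on-drug reference and the drug effect is a constant d, the mean change is (1 − f)d + f × 0 = (1 − f)d. One participant in 100 gives 0.99d; five give 0.95d.

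7. **Effect of closing Visit 3 to post-dose readings.** With a first dose on Day 15, readings on Days 16 to 18 could fill Visit 4 if that is missing, or would stay unmapped. Readings on Days 12 to 14 remain eligible for Visit 3.

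**The case against.** The strongest reply is that little depends on this. Vital signs are not among the key endpoints, nothing is tested, and Conversion Day names a day, so a Day 17 reading is not naturally a conversion-day value. Study drug is dispensed at conversion, so a participant who was dosed will seldom have missed the whole visit. The Intervention label also follows the protocol's schedule, which places the conversion visit under the Intervention Period. All of this stands as to size. It does not remove the gap, because Conversion Day is undefined and the rule leaves Visit 3 open.

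Three stronger readings are tempting, and the documents do not support them.

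- *That the study baseline is contaminated.* SAP 7.2.1 limits it to readings in the Xyrem period up to the night of the first dose, and protocol 9.4.1.2 agrees. Applied by date, an on-XYWAV reading cannot become the study baseline.
- *That never-dosed participants are analysed as treated.* For those who leave in Baseline, 7.2.3 says "prior to the first dose of XYWAV, then data should be mapped to Visit 3". That puts pre-dose data at a pre-dose visit and mixes no drugs. Treatment-emergent event and effectiveness summaries use analysis sets that require at least one XYWAV dose. These participants have no visits after conversion, so they cannot enter the change from conversion. They would appear under Intervention only if the table's label were used to build a by-period vital-signs table, whereas SAP 10.6 specifies tables by visit.
- *That every missing Visit 3 value yields an on-drug reference.* A post-dose unscheduled reading is needed as well.

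**Conclusion.** The concern holds as a minor defect. SAP 7.2.3 classifies the pre-dose Visit 3 in a way that conflicts with SAP 7.2.1 and protocol 9.4.1.2. Its unscheduled-visit rule also permits an on-XYWAV reading to fill a missing Visit 3, even over an equally close Xyrem reading. The consequence is essentially confined to the vital-signs Visit 3 summary and the change from XYWAV Conversion Day.

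The number affected cannot be derived from the documents. Under the assumed ranges it is about 0.1 to 1 participant per 100. Reaching 5 would require 5% missing values and a qualifying unscheduled reading for every one of them. A reader might infer that the before/after comparison of the study as a whole is compromised. It is not, because the key endpoints do not pass through this mapping.

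**What to change.** In SAP 7.2.3:

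- Label pre-dose Visit 3 readings as Baseline (Xyrem).
- Allow only readings taken before the first XYWAV dose to fill Visit 3, and map post-dose unscheduled readings to Visit 4 or later.
- State how an unscheduled reading dated on the first-dose day is handled, for example by clock time relative to the dose where it is recorded.

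In SAP 10.6, define XYWAV Conversion Day as the last value before the first XYWAV dose, so that an earlier pre-dose value serves if the Visit 3 reading is missing.

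The cost is a few lines of SAP text and the matching programming specification. No new data and no protocol change are needed.
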